5.3 Early Discontinuation

If a subject discontinues prematurely, the Investigator will perform Early Termination (ET) visit, capturing the reason for discontinuation.

If a subject does not return for a scheduled visit, every effort will be made to contact the subject and document the End of Study visit assessments. The Investigator must document the primary reason for discontinuation of a study subject in the source document and on the appropriate electronic case report form (eCRF).

Randomized subjects who discontinue due to an adverse event will have all events documented and followed to satisfactory resolution, as detailed in [Section 12](#).

6 INVESTIGATIONAL PRODUCT TREATMENT AND ADMINISTRATION

6.1 Identity of Investigational product(s)

The term *investigational product* is used to refer to the B244 and vehicle drug products. Please see the study *Pharmacy Manual* for full details.

6.2 Investigational Product

Under normal conditions of handling and administration, IP is not expected to pose significant safety risks to site staff. A Material Safety Data Sheet describing the occupational hazards and recommended handling precautions will be provided to site staff if required by local laws or will otherwise be available from the Sponsor upon request.

Investigational product must be stored in a secure area under the appropriate physical conditions for the product. Access to and administration of the IP will be limited to the Investigator and authorized site staff. Investigational product must be dispensed or administered only to participants enrolled in the study and in accordance with the protocol.

The Investigator is responsible for study treatment accountability, reconciliation, and record maintenance. The Investigator or designated site personnel must maintain study treatment accountability records throughout the course of the study. The responsible person(s) will document the amount of study treatment received from and returned to the Sponsor and the amount administered to participants. The required accountability unit for this study will be the bottle. Discrepancies are to be reconciled or resolved.

Product name:	B244, 30ml/bottle	Vehicle, 30ml/bottle
Dosage form:	B244 suspension	Vehicle solution
Unit dose strength:	4x10 ⁹ cfu/ml	50nM Na ₂ HPO ₄ -2mM MgCl ₂ (pH 7.6)
Route/administration/duration:	Topical application BID for 8 weeks	Topical application BID for 8 weeks
Dosing instruction:	4 pumps of spray to saturate the entire face applied BID. Applications should occur in the morning and at night for 8 weeks.	4 pumps of spray to saturate the entire face applied BID. Applications should occur in the morning and at night for 8 weeks.
Physical description:	Odorless, cloudy, light pink suspension	Odorless, clear, and colorless solution

Manufacturer/source of procurement:	AOBiome, LLC	AOBiome, LLC
--	--------------	--------------

6.3 Packaging and Labeling

The investigational product bottles to be dispensed to the subject will be packaged and labeled in accordance with Good Manufacturing Practice. Each individual bottle of the investigational product will be provided in a subject's kit. The contents of the label will be in accordance with all applicable regulatory requirements. B244 and matching vehicle will be packaged in identical 30 ml white bottles.

6.4 Storage of the Investigational product at Site

All investigational drug supplies in the study will be stored in a secure, refrigerated (2-8°C) safe place, under the responsibility of the Investigator or other authorized individual.

The Investigator will maintain temperature monitoring of the investigational product with daily temperature readings. All temperature excursions must be reported to the Sponsor using the Temperature Excursion log. If the investigational product was exposed to the temperature excursion outside the range of 2-8°C, but for the period greater than 24 hours, the investigational product must be quarantined until the Sponsor's approval on future use. Please refer to the *Pharmacy Manual* for additional detail on the Temperature Excursions and temperature monitoring during the shipment and storage at the site pharmacy.

6.5 Treatment Assignment (Randomization)

Randomization will be performed using an Interactive Web Response System (IWRS) at the time the subject has met all eligibility criteria and is ready for enrollment. Subjects will be randomized in a 1:1 ratio to receive either B244 or vehicle and will be stratified by site.

Interactive Web Response System (IWRS) will assign subjects to the treatment arm and specify the kit number to be dispensed.

The randomization scheme will be generated and held by the independent third party throughout the conduct of the study and will not be available to the Sponsor, Investigator, or study staff, or to clinical staff who could have an impact on the outcome of the study.

6.6 Blinding/Unblinding Procedures

This is a double-blind study, thus Sponsor, CRO, site staff, study monitors, and subjects will be blinded to the randomization scheme. The packaging of the investigational product products will be identical in appearance to make difference in treatment less obvious to the subjects.

The blinding scheme for each set of the investigational product will be available to the FDA or other regulatory agency investigators at the time of site inspection to allow for verification of the treatment identity of each subject.

The blinding code must not be broken except in emergency situations for which the identification of the study treatment of a subject is required by the Investigator to complete a serious adverse event report. In such situations, the Investigator will use the IWRS system in order to unblind the treatment for the individual subject. Unblinded information will be held by designated individual(s), and the date and reason for breaking the blind must be recorded and reported appropriately to the IRB.

As the study is blinded, the Investigator should promptly document and explain to the Sponsor and Medical Monitor any premature unblinding (e.g., accidental unblinding, unblinding due to a serious adverse event) of the investigational product(s).

The Investigator may unblind a participant's treatment assignment only in the case of emergency or in the event of a serious medical condition when knowledge of the study treatment is essential for the appropriate clinical management or welfare of the participant, as determined by the Investigator. It is preferred (but not required) that the Investigator first contacts the Medical Monitor to discuss options before unblinding the participant's treatment assignment. The Investigator must notify the Sponsor as soon as possible when a participant's treatment assignment is unblinded without revealing the treatment assignment of the unblinded participant unless that information is deemed important for the safety of participants currently in the study. The date and reason for the unblinding must be documented in the participant's study record.

The Investigator may unblind the treatment assignment for any participant with an SAE. If the SAE requires that an expedited regulatory report be sent to one or more regulatory agencies, a copy of the report, identifying the participant's treatment assignment, may be sent to clinical Investigators in accordance with local regulations and/or Sponsor policy.

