13 MEDICAL MONITOR

13.1 Unblinding due to SAE

Subjects, Investigators, site staff, AOBiome, and the Medical Monitor will be blinded to treatment assignment.

Reasons to unblind Subject should be clearly documented in subject notes, and the monitoring site visit report. In the event of an emergency necessitating unblinding the PI/site staff will make every effort to contact and discuss the event with the Medical Monitor prior to unblinding.

Treatment assignment for an individual subject should be unblinded only in an emergency by the Investigator, when knowledge of the treatment assignment is urgently needed for the clinical management or welfare of the subject. Treatment should be provided in accordance with the medical condition and with regard to the information provided in the Investigator's Brochure.

According to the FDA guidance *Safety Assessment for IND Safety Reporting* IND safety reports submitted should be unblinded. If the blind is broken and a subject with an adverse event that would meet the criteria for reporting as a single event was receiving vehicle, the event will not be reported in an IND safety report because there is a reasonable possibility that the drug did not cause the adverse event but in the event of an SAE determined to be as a result of drug exposure reporting to the FDA will take place.

The Investigator must document the breaking of the code, and the reasons for doing so on the eCRF, in the site file, and in the medical notes.

The Investigator must notify the IRB and the Sponsor in writing as soon as possible following the code break detailing the necessity of the code break, all other members of the research team should remain blinded.

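### Protocol 6.6 lets the investigator unblind any subject with an SAE, which conflicts with its own clinical-need test and with 13.1, and the same person rates causality, severity, IGA and CEA

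*Protocol*

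**What the plan says.** Protocol section 6.6 states the ground for breaking the blind in three ways.

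- The first confines code breaks to "emergency situations for which the identification of the study treatment of a subject is required by the Investigator to complete a serious adverse event report". It is limited to emergencies, but its stated purpose is reporting rather than care.
- The second lets the investigator unblind "only in the case of emergency or in the event of a serious medical condition when knowledge of the study treatment is essential" to the subject's clinical management or welfare.
- The third, at the end of the section, is "The Investigator may unblind the treatment assignment for any participant with an SAE". It has no further condition.

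Section 13.1 gives a fourth statement: "Treatment assignment for an individual subject should be unblinded only in an emergency by the Investigator", and then only where the knowledge is urgently needed for management or welfare.

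The two sections also differ on prior contact with the Medical Monitor. Section 6.6 treats it as desirable but optional. Section 13.1 expects the site to try hard to make contact and discuss the event first.

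**The concern.** A site cannot apply all of these statements to the same case. After an SAE with no clinical need for the code, one sentence permits unblinding and two others forbid it. A monitor or auditor could not say whether such a code break was a deviation.

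The statistical interest is in who becomes unblinded. The investigator breaks the code in the IWRS and is also the rater: of AE severity (12.2), of causality (12.3), of IGA (11.1.6) and of CEA (11.1.7). Safety and tolerability is the primary objective, and treatment-related AEs and SAEs are tabulated separately (Protocol 14; SAP version 2, 8.2.1). Causality also matters for follow-up, because a product-related SAE is a listed reason for discontinuing the subject (5.2). If the arm is known before causality is judged, both the tabulation and the discontinuation decision could be influenced by it.

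**Working it through.** No figure in the plan bears on this point, so the check sets the rules side by side and follows a case through them.

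**The rules compared**

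| Place | Trigger | Need-to-know condition |
|---|---|---|
| 6.6, reporting clause | Emergency | Needed to complete an SAE report |
| 6.6, care clause | Emergency or serious medical condition | Essential to management or welfare |
| 6.6, final paragraph | Any SAE | None stated |
| 13.1 | Emergency only | Urgently needed for management or welfare |

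**Is any SAE wider than the other triggers?** Yes. Under 12.1.2 a hospital admission of any duration makes an event serious. An SAE therefore need not be an emergency, and knowing the arm need not matter to its treatment.

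**A case.** A subject is admitted briefly for an unrelated condition, and nothing in the treatment depends on the arm.

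1. The final paragraph of 6.6 allows the code break.
2. The care clause of 6.6 does not, because the knowledge is not essential.
3. Section 13.1 does not, because there is no emergency and no urgent need.

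**A second conflict.** Take a serious but non-emergency condition where the arm is essential to care. The care clause of 6.6 allows unblinding, while 13.1, read literally, does not. The conflict is therefore not confined to the SAE sentence.

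**What can be affected after the code break?**

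1. Causality and severity of that SAE, if not yet recorded. Nothing in sections 6.6, 12 or 13.1 requires them to be recorded first.
2. Later AE ratings and IGA/CEA scores, if the subject continues. Section 5.2 makes a product-related SAE a reason to discontinue. A subject with an unrelated SAE may stop on other grounds but need not.
3. Section 10 asks for the same investigator or site personnel at each visit where possible. Nothing transfers ratings to a blinded assessor after a code break.
4. The population definitions (SAP version 2, 6.5) and efficacy analysis (8.3) contain no rule for data collected after unblinding.

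**Do the safeguards close the gap?** Section 6.6 has unblinded information held by designated individuals, and 13.1 keeps the rest of the research team blinded. Neither protects the ratings of the investigator who broke the code.

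**Why knowledge of the arm could matter to causality.** Section 13.1 reasons this way itself: an event found to have occurred on vehicle is left out of an IND safety report because the drug may well not have caused it. An investigator who knows the arm could reason likewise when rating.

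**How many subjects?** The number is the count of SAEs followed by a code break that only the final paragraph of 6.6 would allow. The documents give neither an expected SAE count nor a code-break rate, so it cannot be calculated.

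**The case against.** The strongest reply is that this is a wording conflict with little practical effect, surrounded by accountability. Section 6.6 itself treats unblinding because of an SAE as premature unblinding, which the investigator must promptly document and explain to the Sponsor and Medical Monitor. The date and reason are recorded and reported to the IRB. Section 13.1 requires written notice to the IRB and Sponsor setting out why the code break was necessary. Safety reporting is descriptive and all efficacy endpoints are exploratory. Section 1.2.1 reports no drug-attributable SAEs in two acne trials of 36 and 372 subjects.

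Much of this stands. The duties discourage casual use of the permission, and the affected number is probably small. But they operate after the code is broken, so they neither settle which rule applies nor protect the ratings. The acne trials speak to attributed SAEs, while the permission covers any SAE.

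Three stronger readings are tempting, and the documents do not support them.

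- **Spillover through product colour.** B244 is described as "Odorless, cloudy, light pink suspension" and vehicle as clear and colorless (6.2), so a reader might infer that one code break reveals the arms of a whole site: 130/8 = 16.25 or 130/9 = 14.4 subjects, about 11% to 12% of 130. But 6.2 already tells every investigator which product is pink. If colour shows on spraying, arms can be recognised without a code break. If it does not, a code break reveals nothing about other subjects. Any spillover is a separate product-appearance question.
- **The reporting clause as a second open permission.** It is itself confined to emergencies, so it does not contradict an emergency-only rule as the final paragraph does. The problem is its purpose. The reporting minimum in 12.5 names the investigational product, which 6.1 defines as covering both arms, so that item may be completable while blinded. This is not decisive, because the full SAE form is not in the documents.
- **The investigator as the only route to the code for a safety report.** This is not established. An independent third party holds the randomization scheme (6.5), and 6.6 describes treatment-identifying expedited reports being sent to investigators.

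**Conclusion.** The contradiction is real and can be read directly from the text. The final paragraph of 6.6 is wider than the care clause in the same section and wider than 13.1, and those two also differ from each other. A code break that only the final paragraph allows could bias the investigator's causality and severity ratings, and IGA and CEA if the subject continues.

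The size is probably small but cannot be computed. The conclusion assumes only that some SAEs occur without a clinical need for the code, and that an investigator who knows the arm may rate differently. It does not depend on product colour, and it does not imply that such code breaks would go undocumented.

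**What to change.** Reconcile 6.6 and 13.1 into a single unblinding rule, stated once and cross-referenced. It should settle four things:

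- the SAE sentence at the end of 6.6 and the SAE-report clause, so that neither is a separate ground in conflict with the rule;
- whether a serious medical condition short of an emergency qualifies, since 6.6 and 13.1 disagree;
- what is expected about contacting the Medical Monitor first;
- that access for emergencies and subject welfare is left untouched.

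Which clinical threshold the rule carries is for the sponsor and its medical advisers. Deleting the SAE sentence alone would not be enough, because the other differences would remain.

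Add one requirement: the investigator records causality and severity before any code break, where the emergency allows.

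I would not go further on these documents. Routing regulatory unblinding through the third party in 6.5, or sending sites blinded expedited reports, depends on roles, local regulations and sponsor policy that are not shown.

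The cost is protocol wording and one extra documentation step at the time of a code break.

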6.7 Investigational product Dispensation, Application, and Home Storage

At Baseline visit, Subjects will receive a kit containing two 30 ml white bottles. Each bottle will be used for 2 weeks. At Week 4, subjects will return the used bottles from the kit and will be issued a new kit of two 30mL white bottles to be used from Week 4 through Week 8. Subjects will store the unused bottle in the refrigerator until utilized. The bottle which is being used for treatment at a given week may be kept at ambient temperature to be used during the treatment period.

Subjects will be asked not to expose the treatment kit to conditions which are unnatural or harmful to the product, such as excessive heat (temperatures over 77°F (25°C) and freezing temperatures (at 0°C). Subjects may travel with their study medication but should not leave it in the hot car, outside in the cold temperatures etc. Subjects will also be asked not to tamper or cause damage to investigational product bottle.

Each subject will be instructed by the Investigator on proper application technique. The following application instructions will be provided to the subject:

- Subjects will apply 4 pumps of investigational product to saturate their face in the

morning and 4 pumps of investigational product at night.

- Subject should saturate the application area well.
- Subjects will be asked to let the product air dry.
- Subjects may not wash their face for 2 hours post morning application of the investigational product.
- Participants may not bathe, shower or wash their face until morning post evening application of IP.
- While in use, one spray bottle may be stored at ambient temperature. The bottle that is not in current use by the subject, must be stored in the refrigerator.
- DO NOT FREEZE.

6.8 Accountability, Destruction and Return of Study Supplies

In accordance with federal and local regulatory requirements, the Investigator and designated site personnel must document the amount of investigational product dispensed to study Subjects, the amount returned by study Subjects, and amount received and returned to the Sponsor, when applicable. Product accountability records must be maintained throughout the course of the trial. Any quality issue noticed with the receipt or use of an investigational product (deficient investigational product in condition, appearance, pertaining documentation, labeling, expiry date, etc.) should be promptly reported to the Sponsor, who will initiate a complaint procedure.

All investigational product must be stored in a secure locked room with access limited to the Investigator and designated site personnel. Study product is to be stored in a refrigerator between 2-8° C. Maintenance of a temperature log is required.

Under no circumstances will the Investigator allow investigational product to be used other than as directed by this Clinical Trial Protocol, or dispose of investigational product without Sponsor direction.

The Sponsor will supply sufficient quantities of the investigational product for the completion of this study.

The study pharmacist or designated study personnel will maintain an Investigational Materials Accountability Record and a Subject Investigational Product Accountability Log itemizing all investigational product received, dispensed to and returned from each subject during the study. All dispensed bottles must be accounted for, and any discrepancies explained. Study site should contact site Clinical Research Associate (CRA) or designee in case of any dispensing errors or if discrepancies are discovered.

Prior to site closure and at appropriate intervals during the study, site CRA will perform investigational product accountability and reconciliation. At the end of the study, the Investigator will retain all the original documentation regarding investigational product accountability, return, and copies will be sent to the Sponsor.

All unused and used investigational product tubes will be returned to the Sponsor or its designee for destruction at the end of the study.

6.9 Treatment of Investigational Product Overdose

The Sponsor does not recommend specific treatment for an overdose. Washing with conventional cleanser and water will remove the product. The Investigator will use clinical judgment to treat any overdose.

6.10 Dose Changes

No dose changes are anticipated.

7 CONTRACEPTION REQUIREMENTS

7.1 Contraception and Pregnancy Avoidance Measures

Effective contraception is required for all women of childbearing potential (WOCBP) during study participation.

Female subjects must be post-menopausal OR surgically sterile or using highly effective birth control methods (note below) with a negative urine pregnancy test at the Baseline Visit. Male subjects must be willing to not attempt to conceive a child during the participation in the study.

Acceptable forms of contraception include:

Total abstinence; oral (birth control pills), intravaginal (e.g. NuvaRing®), implantable (e.g. Norplant®), injectable (e.g. Depo-Provera®) or transdermal (e.g. Ortho Evra®) contraception, intrauterine device (IUD), double-barrier (diaphragm or condom with spermicidal gel or foam) for one month prior to study enrollment or a vasectomized partner (6 months status post vasectomy).

In case of use of oral contraception women should have been stable on the same pill for a minimum of 30 days before the baseline visit.

If a subject, or female partner of male subject becomes pregnant during the participation in the study, the Investigator will immediately discontinue the Subject from the study and contact the Medical Monitor and the Sponsor. Diligent efforts will be made to determine the outcome for all pregnancy exposures in the clinical trial. Information on the status of the mother and the child will be forwarded to the Sponsor's Safety Team using the Pregnancy Data Collection Form. Generally, follow-up will occur within 6 to 8 weeks following the estimated delivery date. Any premature termination of the pregnancy will be reported. Detailed guidance on the reporting of Pregnancies will be provided in **SAE and Pregnancy Reporting Guidance**.

Payment for all aspects of obstetrical care, child-or related care will be the study participant's responsibility.

